### **11.4 Secondary Outcomes for Clinicians**

We will tabulate the number of phone calls made to patients as a result of the automated alerts, and the actions that were taken. This data will be purely descriptive and hypothesis-generating. If it appears that the automated alerts led to important patient contacts and interventions, further studies could be conducted to evaluate the use of WEBCORE in real time as an additional method of communication between nurses and patients in the post-operative period.

Clinician qualitative impressions of WEBCORE will be gathered at the end of the study during a focus group, at which open-ended questions will be asked (Appendix 6). A Clinician's Satisfaction Survey will be sent out once at the end of the study. This will be filled out by each participating clinician once, and will be summarized descriptively (Appendix 8). Information gathered from the focus group and the exit survey, and will be used towards future development of WEBCORE automated alerts and printed reports.

Clinician impressions of WEBCORE are of interest because they may influence how WEBCORE or a similar system is used clinically. The purpose of this group meeting is to obtain feedback regarding how the WEBCORE system impacted clinician workflow. Physicians and RNs will be asked for specific suggestions regarding how the system could be altered and whether it is perceived as potentially valuable, neutral, or a hindrance to the provision of patient care.

**Memorial Sloan-Kettering Cancer Center  
IRB Protocol**

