**IRB#: 08-155A(8)**

**1.2.2 Secondary Aims**

1. To measure the patient assessments of the usefulness of online symptom self-reporting in the early post-operative period, and clinician perceptions of its potential value in routine outpatient post-operative cancer care.
2. To evaluate the impact of online symptom self-reporting on patient care processes as measured by the number of telephone calls between nurses and patients, resulting interventions (as defined as new appointments scheduled, instructions to the patient to go to Urgent Care, or additions/subtractions/modifications to medications), and patient satisfaction with care delivery.
3. To identify most commonly reported and most distressing symptoms reported by patients after gynecologic cancer surgery and to measure quality of life (QoL) during the immediate postoperative period.

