#### 2.2.2 Secondary Aims

- To measure patient assessments of the usefulness of online symptom self-reporting in the post-operative period, and clinician perceptions of its potential value in routine outpatient post-operative cancer care.
- To evaluate the impact of online symptom self-reporting **on patient care processes as measured by the number of telephone calls between nurses and patients, resulting interventions (as defined as new appointments scheduled, instructions to the patient to go to Urgent Care, or additions/subtractions/modifications to medications), and patient satisfaction with care delivery.**
- To identify most commonly reported and most distressing symptoms reported by patients after gynecologic cancer surgery and to measure quality of life (QoL) during the acute postoperative period.

**Memorial Sloan-Kettering Cancer Center  
IRB Protocol**

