**IRB#: 08-155A(8)**

coverage will be provided by the designated RSA. In that event, the designated RSA will notify the POA of the patient's gynecologic oncologist and the clinic nurse taking patient calls for that gynecologic oncologist that day. No specific responses to these emails will be required, but any actions taken in response to these alerts by clinicians will be tracked (ie, telephone calls, supportive medication prescriptions, new appointments made, etc) using a form emailed to the nurse after the automated email alert (Appendix 5) and the "Ambulatory Care Phone/Email Communication Form" in the EMR. The forms will be collected by the research fellow or by the designated RSA. In addition, a warning popup message will advise the patient that WEBCORE information is not monitored in real-time and therefore to consider calling her physician's office about the symptom of concern.

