## Memorial Sloan-Kettering Cancer Center IRB Protocol

**IRB#: 08-155A(8)**

that triggered the alert. The form will take approximately 5 minutes to fill out. If the nurse indicates that a patient was contacted as a result of the automated email, the research fellow or RSA will look at the “Ambulatory Care Phone/Email Communication Form” in the EMR and record what action was taken. Forms will be collected by the research fellow or RSA. Possible responses include: diagnostic test, prescription, office visit scheduled, UCC visit recommended, no action, other.

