## Memorial Sloan-Kettering Cancer Center IRB Protocol

**IRB#: 08-155A(8)**

[name]], a popup box will appear on the screen recommending that the patient call her physician's office.

In such cases, an automated email alert will be generated by WEBCORE and sent to the primary clinicians (nurse and/or physician) as well as to the coordinating Clinical Research Fellow and designated study RSA. This e-mail will be flagged "urgent" and titled "severe Patient-reported symptom" to ensure prompt response by MSK. No specific clinical response to the alert email will be required. The WEBCORE - generated email will state the following, for example: "*Jane Smith MRN #XXXXXXX*, a patient of *[name]*, reported she vomited "quite a bit", had "very much" constipation, in the last week, potentially serious symptoms, into the WEBCORE online system, at 4:47pm on 8/3/08." Clinicians' responses to the WEBCORE Report will be tracked by the Clinical Research Fellow (Appendix 5).

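### Secondary Aim 2 is measured by calls between nurses and patients, but Section 11.4 tabulates only alert-driven calls made to patients, so the aim's stated measure is not delivered

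*Combined protocol and SAP*

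**What the plan says.** **The aim.** Section 1.2.2 sets out to evaluate the effect of online self-reporting on care processes, "as measured by the number of telephone calls between nurses and patients, resulting interventions" and satisfaction with care. Section 2.2.2 repeats the measure: "on patient care processes as measured by the number of telephone calls between nurses and patients".

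**The analysis.** Section 11.4 states: "We will tabulate the number of phone calls made to patients as a result of the automated alerts", together with the actions taken. It labels these data descriptive and hypothesis-generating. It adds that further studies could follow if the alerts appear to have led to important contacts and interventions.

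**Data capture.** After an alert, the nurse is emailed a report form (Appendix 5). Section 7.5.1 then sets a condition for looking in the EMR communication form: "If the nurse indicates that a patient was contacted as a result of the automated email". Section 9.2.3 repeats it.

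**The popup.** Section 4.2.5 says that, in addition to the alert email, "a warning popup message will advise the patient that WEBCORE information is not monitored in real-time and therefore to consider calling her" physician's office. Section 14.1 is firmer: "a popup box will appear on the screen recommending that the patient call her" physician's office.

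**The concern.** An aim that names its own measure needs an analysis that produces that measure. Here the aim refers to calls between two parties, while the analysis keeps only one direction and one trigger. The omitted calls are not incidental, since the popup suggests that patients make one. If a patient telephones first, the nurse may have no reason to call out, and the tabulated count could then be lower even though contact took place.

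What is at stake is the reporting of a secondary aim. A reader told that Aim 2 was assessed would expect a count of nurse-patient calls and would be given a subset. The condition on opening the EMR form also means that the missing calls would not be abstracted, so the gap could be closed later only by going back to the charts.

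**Working it through.** The documents give no figure for this measure, so there is none to reproduce. The check sets the texts side by side.

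1. **Scope of the aim (1.2.2, 2.2.2).** Calls between nurses and patients. The word *all* is not used, but neither direction nor trigger is restricted.
2. **Scope of the analysis (11.4).** Calls made to patients, and only those resulting from an alert. This is narrower in two respects: outbound only and alert-driven only.
3. **Other sections that might fill the gap.** Sections 9.2, 11.2 and 11.3 plan no count of patient-initiated calls. The backup calls in 9.1 and 11.2 are research calls to patients who did not log in, made by the research fellow (4.1). They are not nurse-patient care calls.
4. **Capture (7.5.1, 9.2.3).** The nurse form follows an alert, and the EMR form is opened only after the nurse attributes a contact to that alert. The listed responses are diagnostic test, prescription, office visit, Urgent Care visit, no action and other. None is specifically a call from the patient.
5. **Would an inbound call be a nurse-patient call?** Yes, by day. The account of the usual post-operative course in Section 3 says a patient with a problem calls the surgeon's nurse, or at night the fellow on call. A daytime call after the popup therefore falls within Aim 2 and outside 11.4.
6. **Do popup and alert share a trigger?** Yes. Sections 4.2.5 and 14.1 attach both to the same severe response.

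**Size.** Let q be the share of nurse-patient calls in the study interval that are inbound or not alert-driven. Section 11.4 then captures 1 − q of the calls the aim describes. The documents do not give q. For assumed values:

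| Assumed q | Share captured, 1 − q |
|---|---|
| 10% | 90% |
| 25% | 75% |
| 50% | 50% |
| 75% | 25% |

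This range is illustrative only; nothing in the documents favours one row over another.

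**The case against.** The strongest reply is that 11.4 asks a narrower question of its own: whether alerts sent to nurses led to important contacts and interventions. For that question, clinician calls made because of an alert are the right count, and mixing in patient-initiated calls would blur it. This stands. A reader might infer that the 11.4 count is biased downward; for the alert question it is not. The fault is that the aim is broader than its analysis.

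A reader might also infer that a call made after the popup is an effect of WEBCORE. The documents do not support that. Patients are trained to telephone about severe symptoms just as they would without the system (training session, Section 4.2.1), and calling the nurse is usual care. In a single arm, such a call cannot be attributed to the popup.

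A third tempting step is to size the gap from the earlier chemotherapy study in Section 3.5, where 42 alerts prompted seven telephone contacts: 7/42 = 16.7%, leaving 42 − 7 = 35 alerts that might have been followed by an unrecorded call. That would place the true share anywhere from 17% to 100%, which is a logical bound and not an estimate. Section 3.5 does not give the direction of the seven contacts or say whether a popup was shown. The alerts came from only 16 patients, so one call could answer several alerts. The same section describes surgical patients as a different group.

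Finally, the nurse form's text is not available here, and its *other* category might hold some inbound contacts. That is possible, but no count of them is planned.

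**Conclusion.** The mismatch holds: the tabulation planned in 11.4 does not deliver the measure named in Aim 2, and the capture rule means patient-initiated calls would not be abstracted. The conclusion rests on reading *between nurses and patients* as covering either direction, which is its ordinary sense, and on no other section planning the count.

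The extent of the shortfall is unknown. The consequence is modest, because the outcome is secondary and descriptive with no threshold attached, and the responder rule for the primary conclusion does not depend on it. It is still worth correcting, because aligning the aim with its analysis is inexpensive.

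**What to change.** Choose one of two routes.

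- **Widen the analysis.** In 11.4, have the fellow or RSA check the EMR communication form after every alert, whatever the nurse's report says, and for all enrolled patients over the study interval if feasible. Tabulate nurse-patient calls by direction and by timing relative to an alert, using a window that the sponsor sets in advance. Keep alert-triggered outbound calls as a separate subset, so that the existing alert question is still answered. Amend 7.5.1 and 9.2.3 to match.
- **Narrow the aim.** Reword Aim 2 in 1.2.2 and 2.2.2 to alert-triggered outbound calls and leave 11.4 as it is.

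Under either route, describe the result as call volume and alert-linked contacts instead of impact, because a single-arm study has no comparator.

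**Cost.** Narrowing the aim is a wording change. Widening the analysis adds modest chart abstraction by staff who already use this form. Checking after every alert is the lighter option. Reviewing every enrolled patient (110 planned) is more work, and Section 11.1 ties the sample size to one dedicated fellow, hence the feasibility condition. Before choosing, the sponsor should confirm that the EMR form records inbound calls, including night calls to the fellow, and state whether those night calls count towards the measure.

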**IRB#: 08-155A(8)**

**11.5 Missing Data**

The WEBCORE system allows patients to skip individual items when completing the online form. Therefore, we will tabulate the number of missing items from each of the included questionnaires in this study (BPI, QLQ-C30, and CTCAE). These will be reported descriptively, to assess if any particular items are skipped with excess frequency compared to others. Based on prior WEBCORE studies, however, we anticipate that the frequency of skipped individual items will be very low (~1%). In addition, as a part of the overall feasibility evaluation, we will tabulate the frequency with which patients fail to complete the entire form on schedule.

**12.0 RESEARCH PARTICIPANT REGISTRATION PROCEDURES**

**12.1 Research Participant Registration**

Confirm eligibility as defined in the section entitled Criteria for Patient/Subject Eligibility.

Obtain informed consent, by following procedures defined in section entitled Informed Consent Procedures.

During the registration process registering individuals will be required to complete a protocol specific Eligibility Checklist.

All participants must be registered through the Protocol Participant Registration (PPR) Office at Memorial Sloan-Kettering Cancer Center. PPR is available Monday through Friday from 8:30am-5:30pm at [contact]. Registrations must be submitted via the PPR Electronic Registration System (<http://ppr/>). The completed signature page of the written consent/RA or verbal script/RA, a completed Eligibility Checklist and other relevant documents must be uploaded via the PPR Electronic Registration System.

**13.0 DATA MANAGEMENT ISSUES**

A dedicated Clinical Research Fellow and a Research Study Assistant (RSA) will be assigned to this study. The responsibilities of the Clinical Research Fellow will include project compliance, data collection, abstraction and entry, data reporting, regulatory monitoring, problem resolution and prioritization, and coordination of the activities of the protocol study team. The responsibilities of the Surgery RSA will include project compliance, data collection, and abstraction and entry.

The data collected for this study will be entered into a secure database. Source documentation will be available to support the computerized patient record.

## Memorial Sloan-Kettering Cancer Center IRB Protocol

**IRB#: 08-155A(8)**

### 13.1 Quality Assurance

Weekly registration reports will be generated to monitor patient accruals and completeness of registration data. Routine data quality reports will be generated to assess missing data and inconsistencies. A log of all eligible patients will be maintained. Accrual rates and extent and accuracy of evaluations and follow-up will be monitored periodically throughout the study period and potential problems will be brought to the attention of the study team for discussion and action.

Random-sample data quality and protocol compliance audits will be conducted by the study team, at a minimum of two times per year, more frequently if indicated.

### 13.2 Web Security

This study will use the WEBCORE online platform which was developed at MSKCC and has previously undergone privacy and security review. The current design for the WEBCORE system architecture is reproduced in a diagram in Appendix 7. This configuration has been developed with input from and review by computer security/privacy experts in the MSKCC Information Systems office and is designed to assure that WEBCORE conforms with current MSKCC and HIPAA standards for the protection of PHI. A Security Evaluation Peer Working Group (SEPWG) form has previously been reviewed by the MSKCC Information Security Department outlining the configuration and functionality of the WEBCORE system. WEBCORE is currently being used in MSKCC protocols 04-020 and 07-034 (CALGB 70501).

Patient data collected through WEBCORE will be stored in the secure MSKCC Clinical Research Database (CRDB). Access to data will be password protected, and user-level access will be controlled to allow access to a specific patient's data only for clinicians and research staff responsible for that specific patient. Data will only be reviewed by staff when directly related to patient care or conduct of this study.

### 13.3 Data and Safety Monitoring

The Data and Safety Monitoring (DSM) Plans at Memorial Sloan-Kettering Cancer Center were approved by the National Cancer Institute in September 2001. The plans address the new policies set forth by the NCI in the document entitled "Policy of the National Cancer Institute for Data and Safety Monitoring of Clinical Trials" which can be found at: <http://cancertrials.nci.nih.gov/researchers/dsm/index.html>. The DSM Plans at MSKCC were established and are monitored by the Office of Clinical Research. The MSKCC Data and Safety Monitoring Plans can be found on the MSKCC Intranet at: <http://mskweb2.mskcc.org/irb/index.htm>

There are several different mechanisms by which clinical trials are monitored for data, safety and quality. There are institutional processes in place for quality assurance (e.g., protocol monitoring, compliance and data verification audits,

**Memorial Sloan-Kettering Cancer Center  
IRB Protocol**

**IRB#: 08-155A(8)**

therapeutic response, and staff education on clinical research QA) and departmental procedures for quality control, plus there are two institutional committees that are responsible for monitoring the activities of our clinical trials programs. The committees: *Data and Safety Monitoring Committee (DSMC)* for Phase I and II clinical trials, and the *Data and Safety Monitoring Board (DSMB)* for Phase III clinical trials, report to the Center's Research Council and Institutional Review Board.

During the protocol development and review process, each protocol will be assessed for its level of risk and degree of monitoring required. Every type of protocol (e.g., NIH sponsored, in-house sponsored, industrial sponsored, NCI cooperative group, etc.) will be addressed and the monitoring procedures will be established at the time of protocol activation.

#### **14.0 PROTECTION OF HUMAN SUBJECTS**

As this is an observational quality of life study of the impact of treatment on QOL, it is unlikely that there will be any adverse effects due to this protocol. Participation is voluntary and the protocol will not interfere with routine treatment. It is possible that patients may experience distress when answering questions. Any participant who demonstrates severe depressive symptoms or requests counseling will be referred for counseling. Participants can withdraw at any time. Information for each participant will be recorded using a unique identification number in a separate database. This number will not be linked to personal data which may compromise the anonymity of the participant. Access to the database will be limited to the research team. All participants will be 18 years or older. Each participant will be required to sign an informed consent prior to completing the baseline questionnaire. Consent forms will be signed by a consenting professional upon enrollment at which time all questions may be answered. There will be no financial burden incurred by participants.

## Memorial Sloan-Kettering Cancer Center IRB Protocol

**IRB#: 08-155A(8)**

[name]], a popup box will appear on the screen recommending that the patient call her physician's office.

In such cases, an automated email alert will be generated by WEBCORE and sent to the primary clinicians (nurse and/or physician) as well as to the coordinating Clinical Research Fellow and designated study RSA. This e-mail will be flagged "urgent" and titled "severe Patient-reported symptom" to ensure prompt response by MSK. No specific clinical response to the alert email will be required. The WEBCORE - generated email will state the following, for example: "*Jane Smith MRN #XXXXXXX*, a patient of *[name]*, reported she vomited "quite a bit", had "very much" constipation, in the last week, potentially serious symptoms, into the WEBCORE online system, at 4:47pm on 8/3/08." Clinicians' responses to the WEBCORE Report will be tracked by the Clinical Research Fellow (Appendix 5).

### 14.2 Privacy

This study will involve the collection of confidential patient self-reports of HRQL and symptoms over the Internet. Security and privacy precautions have been taken in the design of the WEBCORE online platform. Patient data collected via WEBCORE will be stored in the secure MSKCC Clinical Research Database (CRDB). User-level access to data will be password protected, and only individual patients, appropriate clinical staff, and research study staff will have access to data.

MSKCC's Privacy Office may allow the use and disclosure of protected health information pursuant to a completed and signed Research Authorization form. The use and disclosure of protected health information will be limited to the individuals described in the Research Authorization form. A Research Authorization form must be completed by the Principal Investigator and approved by the IRB and Privacy Board.

### 14.3 Serious Adverse Event (SAE) Reporting

Only SAEs related to using the online **WEBCORE** system will be reported to the IRB. Any SAE must be reported to the IRB/PB as soon as possible but no later than 5 calendar days. The IRB/PB requires a Clinical Research Database (CRDB) SAE report be submitted electronically to the SAE Office at [[contact]](mailto:[contact]). This report should contain the following information:

Fields populated from CRDB:

- Subject's name (generate the report with only initials if it will be sent outside of MSKCC)
- Medical record number
- Disease/histology (if applicable)

**Memorial Sloan-Kettering Cancer Center  
IRB Protocol**

**IRB#: 08-155A(8)**

- Protocol number and title

Data needing to be entered:

- The date the adverse event occurred
- The adverse event
- Relationship of the adverse event to the treatment (drug, device, or intervention)
- If the AE was expected
- The severity of the AE
- The intervention
- Detailed text that includes the following information:
  - A explanation of how the AE was handled
  - A description of the subject's condition
  - Indication if the subject remains on the study
  - If an amendment will need to be made to the protocol and/or consent form

The PI's signature and the date it was signed are required on the completed report.

